6.1.3. Follow-up Period (Day 86 - Day 180)

Subjects will return to the site for follow-up visits on Days 86 and 180 following Baseline. Each follow-up visit should occur within ± 15 days of the planned date.

The evaluations that will occur during the Follow-up Period (Days 86 and 180) include the following: acute GVHD staging, physical exam (Day 180 only), ECG (Day 180 only), vital signs, weight, laboratory tests, pregnancy test (for women of childbearing potential), PK/PD (see Table 5), antibodies to ALXN1007, exploratory biomarkers, and recording of AEs (see Section 11.2) and concomitant medications and therapies (see Section 8.2).

6.1.4. Survival Status on Day 360

Subjects and/or their caregivers will be contacted by the site on Day 360 (± 15 days) following Baseline. Questions regarding the subject's survival status will be asked of the subject and/or the caregiver by telephone call.

6.1.5. Early Termination Visit

An ET visit will be conducted when the following occur:

- In the event that the biopsy results do not confirm GI GVHD, study treatment will be discontinued, and an ET visit will be performed 6 weeks after the last dose of ALXN1007 was received.
- If the subject discontinues for any reason after receiving at least 1 dose of ALXN1007 and before the Day 180 visit, the ET visit should be performed (within 5 days) if possible.

The ET visit assessments will include acute GVHD staging, physical exam, ECG, vital signs, weight, various laboratory tests, PK/PD, antibodies to ALXN1007, exploratory biomarkers, and recording of AEs (see Section 11.2) and concomitant medications and therapies (see Section 8.2).

Note: Subjects must continue antibiotic prophylaxis active against meningococcal infection for 6 weeks after the last dose of ALXN1007.

6.1.6. Missing Visits

Subjects who are unable to complete a scheduled visit must be contacted by the site study staff to determine the reason. For subjects who miss a dose, the Investigator is responsible for discussing the status and future treatment of these subjects with the Alexion Medical Monitor. Every effort must be made to undertake the protocol-specified evaluations through Day 180.

Follow-up due diligence and documentation are discussed in Section 7.3.2.

6.2. Number of Subjects

Up to 36 subjects confirmed by biopsy to have GI GVHD will be enrolled in this study. For the 10 mg/kg QW dosing cohort (Cohort 1), a maximum of 18 subjects will be enrolled. For Cohorts 2 and 3, and any other dosing cohorts that may be added, a minimum of 3 up to a maximum of approximately 6 subjects will be enrolled in each cohort.

6.3. Treatment Assignment

All subjects meeting the inclusion and exclusion criteria for the study will receive ALXN1007 over an 8 week treatment period. The first dosing cohort (Cohort 1) will receive 10 mg/kg ALXN1007 administered IV QW for 8 weeks. With approval of Amendment 6, Cohort 2, 20 mg/kg QW for 8 weeks, will be added to the study. An additional cohort, 20 mg/kg twice weekly for 8 weeks (Cohort 3), is planned after DMC review of safety and tolerability data at Day 28 on the first 3 patients in Cohort 2. The planned dosing cohorts in this study are summarized in Table 6.

Dosing Cohort ¹	Total ALXN1007 Dose per Week	Dosing Regimen	Infusion Duration	Sample Size
1	10 mg/kg	10 mg/kg QW (8 total doses)	1 hour ± 10 minutes	18 (maximum)
2	20 mg/kg	20 mg/kg QW (8 total doses)	2 hours ± 10 minutes	3 to approximately 6 ²
3	40 mg/kg	20 mg/kg twice weekly (16 total doses)	2 hours ± 10 minutes	3 to approximately 6 ²

Table 6: Planned ALXN1007 Dosing Cohorts

Details on allowance for dose adjustments, as well as stopping rule criteria for ALXN1007 dosing, can be found in Section 6.4.

6.4. Dose Adjustment and Stopping Criteria

6.4.1. Dose Adjustment Criteria

For subjects who are unable to tolerate weekly doses of 20 mg/kg or higher, dose reduction to a minimum of 10 mg/kg weekly may be permitted after discussion between the Principal Investigator and the Alexion Medical Monitor. For subjects unable to tolerate the minimum weekly dose of 10 mg/kg QW, ALXN1007 treatment will be discontinued.

If ALXN1007 treatment is prematurely discontinued, procedures for continued follow-up outlined in Section 7.3.2 must be followed.

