5. STUDY OBJECTIVES AND ENDPOINTS

5.1. Objectives

The objectives of this trial are to evaluate the safety, tolerability, PK/PD, and efficacy of IV ALXN1007 administered over an 8 week treatment period in subjects with acute GVHD of the lower GI tract.

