7.3. Subject Withdrawal Criteria

The Investigator should notify the Sponsor and their site monitor of all study withdrawals as soon as possible.

Subjects may withdraw consent at any time. Every effort should be made to ensure subjects are willing to comply with study participation prior to conducting the screening procedures and the subject should be fully informed of the restrictions related to the change of concomitant medications during the study.

Investigators may choose to discontinue a subject's treatment because of an AE as well as conditions or illnesses that preclude compliance with the protocol from the standpoint of the subject's safety or well-being (safety, behavioral or administrative reasons).

Subjects should be permanently discontinued from ALXN1007 treatment if any of the following occur during the study:

- Serious infusion reaction (such as bronchospasm with wheezing or requiring ventilatory support or symptomatic hypotension, refer to Section 9.5.1) or serum sickness-like reactions manifesting 1 to 14 days after drug administration;
- A Grade 4 AE related to study treatment;
- Severe uncontrolled infection;
- Malignancy other than non-melanoma skin cancer or relapse of the disease for which the bone marrow transplant was performed;
- Meningococcal infection;
- Initiation of protocol prohibited medications;
- Pregnancy or planned pregnancy; or
- If the Alexion Medical Monitor and/or the Investigator deem it is in the best interest of the subject (eg, the subject is unable to tolerate the minimum ALXN1007 dose for the study; see Section 6.4.1).

Subjects who withdraw, or are withdrawn, from the study will not be replaced with a newly enrolled subject, with the exception of subjects who do not have biopsy confirmation of GI GVHD (see Sections 6.1.5 and 7.3.2).

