#### **7.3.1. Study Duration, Treatment Compliance, and Exposure**

For each dosing visit, number (%) of patients with study treatment administered, total dose (mg) will be summarized by descriptive statistics. The study dose (mg) will be calculated as 5×mL administered when incomplete dose is administered, note that per pharmacy manual, the final conc. is 5mg/ml.

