**Table 4. Subcategories For Treatment-Emergent Adverse Events (TEAEs)**

Relationship: Related AEs (possibly, probably, or definitely related), Not Related AEs (not related or unlikely)
Severity: Grade 1,2,3,4,5
Leading to withdrawal

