**7.3.2.5. Deaths, Other SAEs and Other Significant Adverse Events**

Summaries of TEAEs leading to death will be provided by SOC and PT. Summaries of TEAEs leading to study treatment discontinuation will be provided by SOC and PT.

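### Intolerance can lead to dose reduction at 20 mg/kg per week or more but ends treatment at 10 mg/kg once weekly, so the SAP's withdrawal and discontinuation displays are not comparable across cohorts

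*Protocol*

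**What the plan says.** Tolerability is a named objective: Protocol 5.1 sets out to "evaluate the safety, tolerability, PK/PD, and efficacy of IV ALXN1007".

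Protocol 6.4.1 treats intolerance differently by dose. The rule for the higher doses begins "For subjects who are unable to tolerate weekly doses of 20 mg/kg or higher, dose reduction to a minimum of 10 mg/kg weekly", and it makes that step optional, once the investigator and the sponsor's medical monitor have discussed it. At the lowest dose there is no further step: "For subjects unable to tolerate the minimum weekly dose of 10 mg/kg QW, ALXN1007 treatment will be discontinued". Some rules apply at every dose. Protocol 7.3 requires permanent discontinuation for, among other things, "A Grade 4 AE related to study treatment" and serious infusion reactions. Protocol 6.4.2 adds rules for holding doses.

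SAP section 7 tabulates results by regimen. By dosing action, it plans two adverse-event displays. One is the overview category "Leading to withdrawal" in SAP Table 4. The other is in SAP 7.3.2.5: "Summaries of TEAEs leading to study treatment discontinuation will be provided by SOC and PT". No summary covers reductions or holds, and no rule says how a dose-reduced subject is displayed.

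For exposure, SAP 7.3.1 gives the number and percentage dosed at each dosing visit, and "total dose (mg) will be summarized by descriptive statistics". Its title includes treatment compliance, which Protocol 13.5 promises for all subjects, but it defines no measure relative to the assigned dose.

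**The concern.** A discontinuation for intolerance does not mean the same thing in each column. In Cohort 1 it is the only outcome that 6.4.1 provides. In Cohorts 2 and 3 it is what remains after some subjects may have been kept on treatment at a lower dose. Those subjects appear in neither display by dosing action. A reader who compares discontinuation across regimens would be comparing two different quantities.

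At stake is how the study report describes tolerability by dose. A Cohort 3 row with no discontinuations could mean that the regimen was tolerated, or that some subjects finished on less than the assigned dose. The two displays alone do not separate these.

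**Working it through.** **Inputs.** Cohort 1 has at most 18 subjects, and Cohorts 2 and 3 have 3 to about 6 each (Protocol 6.2). The documents give no intolerance rate, no reduction rate and no power or precision statement for tolerability, so there is no figure of the plan's own to reproduce. Everything below is illustration under stated assumptions:
- p: true share of subjects who cannot tolerate the assigned dose, the same in every cohort unless stated.
- f: share of intolerant subjects at 20 mg/kg per week or more who stay on a reduced dose and do not later stop.
- Body weight for the exposure check: mean 80 kg, SD 18 kg.

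**Step 1: expected discontinuation rate.** Cohort 1: p. Cohorts 2 and 3: p(1 − f).

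| p | Cohort 1 | Cohorts 2/3, f = 0 | f = 0.5 | f = 0.8 |
|---|---|---|---|---|
| 10% | 10% | 10% | 5% | 2% |
| 20% | 20% | 20% | 10% | 4% |
| 30% | 30% | 30% | 15% | 6% |
| 40% | 40% | 40% | 20% | 8% |

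Because f cannot be negative, the higher-dose rate can equal or fall below p, but cannot exceed it. The same formula shows that a real difference can be masked: with 20% intolerance in Cohort 1, 40% in Cohort 3 and f = 0.5, the display reads 20% against 0.40 × 0.5 = 20%.

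**Step 2: chance of no discontinuation in a higher-dose cohort of n**, (1 − p(1 − f))^n, at p = 20%:
- n = 6: 0.80^6 = 26% (f = 0); 0.90^6 = 53% (f = 0.5); 0.96^6 = 78% (f = 0.8).
- n = 3: 0.80^3 = 51%; 0.90^3 = 73%; 0.96^3 = 89% (88.5% before rounding).

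**Step 3: does total mg per visit reveal a reduction?** Take six subjects at 20 mg/kg.
- The mean is 20 × 80 = 1,600 mg. If one 80 kg subject is halved, it is (5 × 1,600 + 800)/6 = 1,467 mg. The drop of 133 mg is less than one standard error, 20 × 18/√6 = 147 mg.
- The minimum does better in that case. An unreduced subject would have to weigh 40 kg to read 800 mg, which is (80 − 40)/18 = 2.2 SD below the mean.
- The minimum is not reliable for heavier subjects. A 120 kg subject reduced to 10 mg/kg reads 1,200 mg, the same as a 60 kg subject on 20 mg/kg, who is only (80 − 60)/18 = 1.1 SD below the mean.
- A Cohort 3 subject reduced to 20 mg/kg once weekly shows unchanged mg at each dosed visit. The only trace is a lower number dosed at the other weekly visit, which looks the same as a hold or a missed visit.

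**Step 4: after the fix.** If reductions and discontinuations are counted together, the expected rate is p in every cohort, whatever f is. At p = 20% that is 0.20 × 18 = 3.6 subjects in Cohort 1 and 0.20 × 6 = 1.2 in a higher-dose cohort of 6. The chance of none in 6 returns to 26%.

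**The case against.** The strongest reply is that safety is not judged on these two displays. SAP 5.2 rests it on the incidence and severity of TEAEs, on SAEs and on other measures. SAP 7.3.2.2 to 7.3.2.4 tabulate TEAEs and SAEs by SOC and preferred term, relationship and grade, whatever was done with the dose. This stands. A reader might infer that the SAP measures intolerance only through discontinuation, but the SAP defines no intolerance measure, and the reduction rule does not itself shift those main tables. What they do not show is which events cost a subject the assigned dose.

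Second, reductions and holds are not invisible. The number dosed per visit would show a skipped infusion, the minimum and maximum would sometimes show a halved dose, and SAP 4.1 promises by-patient listings of all data. In cohorts of 3 to about 6, a listing can be read by eye. It would be too strong to say that the exposure data cannot show a reduction; they show it indirectly and not reliably.

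Third, reduction is discretionary, and several rules end treatment at every dose: the Protocol 7.3 criteria, and anaphylaxis or a recurrent infusion reaction under 9.5.1. This limits f. A contrast of 20% against 0% needs f = 1, the extreme case, and nothing in the documents supports it.

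Fourth, the study is non-randomised, small, descriptive and terminated early, and Protocol 14.4 bases escalation on DMC review of aggregate data, not on these tables. That reduces the consequence. It does not make the two displays mean the same thing in each column, and the SAP does not mark SAP Table 4, 7.3.2.5 or 7.3.1 as dropped for the abbreviated report.

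**Conclusion.** The point holds for two displays: TEAEs leading to withdrawal and TEAEs leading to treatment discontinuation. For equal intolerance they are not comparable between Cohort 1 and the higher-dose cohorts, and the error can only favour the higher doses. Its size depends on p and f, which the documents do not give. At p = 20% it runs from nothing (f = 0) to a rate of 4% in place of 20% (f = 0.8).

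The documents do not support reading this as a bias in the safety results as a whole. Nor do they support the inference that the higher cohorts exist to compare tolerability: Protocol 4.4 adds them because 10 mg/kg weekly might not suppress C5a enough. With so few subjects, any comparison between cohorts is imprecise in any case. This is a cheap improvement to reporting on a named objective.

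**What to change.** - **SAP Table 4 and 7.3.2.5:** add, by assigned cohort, the number and percentage of subjects with a dose reduction or permanent discontinuation for an adverse event or intolerance. Show reduction, hold and discontinuation as separate rows beneath it.
- **SAP 7.3.1:** summarise administered dose in mg/kg and as a percentage of the assigned dose. For Cohort 3, include a weekly total, so that a change from two infusions to one is visible.

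The dose summaries need only dosing records and the weights already scheduled weekly in Protocol Tables 3 and 4. The counts also need the reason for each change in dosing. The documents do not show whether the eCRF records this for each adverse event; if it does not, the reason would have to come from other records.

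The cost is SAP wording and one or two descriptive tables, and the higher cohorts may look less well tolerated than under the present displays. Flagging dose-reduced subjects in the response tables is optional. The clinical rules in Protocol 6.4.1 and 6.4.2 stay as they are.

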6.4.2. Safety Criteria for Stopping Doses

For all subjects (irrespective of ALXN1007 dose), if an adverse reaction occurs during the administration of ALXN1007, the infusion may be slowed or stopped at the discretion of the Principal Investigator (PI). If the infusion is slowed or temporarily stopped, **the total infusion time should not exceed 3 hours**. The adverse reaction must be recorded on the AE page of the electronic case report form (eCRF).

Infusion of other monoclonal antibodies has been associated with infusion reactions, with onset typically during or shortly after completion of the infusion. For this reason, subjects will be carefully observed during each infusion. Subjects will remain under observation for 2 hours after the infusion. Advice on management and prevention of infusion reactions is included in Section 9.5.1.

If a subject experiences a **Grade 4 AE related** to study treatment, ALXN1007 treatment should be permanently discontinued (see Section 7.3).

Treatment with ALXN1007 should be held if any of the following occurs:

• If a subject experiences a **Grade 3 AE related** to study treatment; or

At the discretion of the Sponsor, and in consultation with the DMC, other dosing cohorts (not to exceed a total dose of 40 mg/kg per week) may also be explored based on cumulating safety and tolerability data as well as any PK/PD data that may be available.

² For Cohorts 2 and 3 (and any other dosing cohorts that may be added), a minimum of 3 up to a maximum of approximately 6 subjects may be enrolled.

- If a subject experiences a **Grade 4 AE unrelated** to study treatment; or
- If a subject experiences an acute infection that is either not identified or controlled by the next scheduled infusion.

The PI should discuss the AE/acute infection as soon as possible with the Sponsor before resuming ALXN1007 treatment. Treatment with ALXN1007 may be resumed once the AE/acute infection has resolved, stabilized or returned to baseline. There should be a minimum of 4 days between ALXN1007 doses for subjects receiving weekly treatment. For subjects receiving twice weekly treatment, there should be a minimum of 2 days between ALXN1007 doses. If the recommended acceptable visit windows cannot be observed (see Section 6.1.2), the Sponsor Medical Monitor or designee must be contacted.

6.5. Criteria for Study Termination

6.5.1. End of Study for an Individual Patient

Study participation will end for each individual subject at Day 360. The last clinic visit will be at the Day 180 Visit, and the subject's survival status will be collected on Day 360 via telephone contact.

6.5.2. End of Study for All Patients

The study will end when all treated subjects have either completed the Day 360 data collection, the ET visit, or are documented as lost to follow-up.

6.5.3. Study Termination by Sponsor

The Sponsor may terminate this study at any time for any reason including, for example, clinical or administrative reasons.

6.5.4. Stopping Guidelines for Excessive Mortality

Mortality of 40% at Day 56 would be considered unexpected and an unacceptable number of excess deaths compared to the anticipated and historical rate of approximately 20% (data on file). Therefore, a stopping rule for Day 56 mortality will be applied after every 6 subjects are accrued. The study will be stopped at interim evaluation (t) if the number of deaths is ≥Xt, eg, if 4 or more deaths in the first 6 subjects or 6 or more deaths in the first 12 subjects, etc, as detailed in Table 7 below. A 20% mortality rate, which is anticipated based on historical data, will have a 2.6% chance of triggering the stopping rule for mortality. If a mortality rate of 40% is observed, a 20% increase in mortality over the historical rate, there will be a 71.0% chance of triggering the stopping rule with 30 subjects.

Table 7: Cumulative Stopping Probabilities for Mortality Rates at Day 56

Evaluation (t)	Total N	Xt	Cumulative Probabilities of Stopping at Evaluation (t) with Observed Mortality Rates					
			0.20	0.40				
1	6	4	1.7%	17.9%				
2	12	6	1.9%	33.5%				
3	18	8	1.6%	43.7%				
4	24	10	1.3%	51.0%				

Evaluation (t)	Total N	Xt	Cumulative Probabilities of Stopping at Evaluation (t) with Observed Mortality Rates					
			0.20	0.40				
5	30	11	2.6%	71.0%				

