13.1. General Considerations

All data collected during the study will be presented in summary tables, figures and/or by-subject data listings. Continuous variables will be summarized using mean, standard deviation (SD), median, minimum and maximum. Categorical variables will be summarized using percentages and frequency distributions. Graphical displays will be presented as appropriate.

A stopping rule for excess mortality at Day 56 will be applied after every 6 subjects are accrued. The stopping guidelines for excess mortality will be applied as described in Section 6.5.4.

A brief interim safety report summarizing AEs and SAEs will be generated when the first six subjects have completed the day 86 visit. Additionally, an informal interim analysis will occur after all subjects have completed Day 56, which is the end of the treatment period. This interim analysis will summarize the primary endpoint and other efficacy endpoints with the exception of overall survival and non-relapse mortality. In terms of safety, all treatment emergent adverse events (TEAEs), infections, neutropenia and infusion reactions will be summarized. The interim analyses will also summarize PK and PD results. Additional informal interim analyses may be conducted based on regulatory requests and/or Sponsor discretion. A final analysis will be conducted at study completion.

Efficacy and safety analyses will be performed using SAS for Windows, Version 9.2 or higher (SAS Institute Inc., Cary, NC, USA).

No formal hypothesis testing will be performed. Efficacy data will be analyzed using descriptive statistics. All analysis tabulations will be presented by dose across the full range of doses actually examined in the study.

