## 7.4. Interim Analyses

The following interim data analyses will be performed during the study.

- This study has a stopping guideline for excessive mortality (refer protocol Section 7.5.2). A stopping rule for Day 56 mortality will be applied after every 6 patients are accrued. The study will be stopped at interim evaluation (t) if the number of deaths is  $\geq X_t$ , e.g., if 4 or more deaths in the first 6 patients or 6 or more deaths in the first 12 patients, etc., as detailed in Table 4 below. A 20% mortality rate, which is anticipated based on historical data, will have a 2.6% chance of triggering the stopping rule for mortality. If a mortality rate of 40% is observed, a 20% increase in mortality over the historical rate, there will be a 71.0% chance of triggering the stopping rule with 30 patients.

At every interim evaluation (t); a listing for patients who died including the cause of death will be produced along with any other data points deemed required.

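### The Day 56 mortality looks are triggered by accrual with no follow-up condition, while the boundaries and their printed probabilities assume that every subject's Day 56 outcome is known; those probabilities are also single-look values labelled cumulative.

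*Protocol*

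**What the plan says.** The look is tied to accrual in three places. Protocol 6.5.4: "a stopping rule for Day 56 mortality will be applied after every 6 subjects are accrued". Protocol 13.1: "A stopping rule for excess mortality at Day 56 will be applied after every 6 subjects are accrued". SAP 7.4: "A stopping rule for Day 56 mortality will be applied after every 6 patients are accrued". The protocol synopsis says the same.

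The boundary is a count of deaths among the first N subjects: "if 4 or more deaths in the first 6 subjects or 6 or more deaths in the first 12 subjects", then 8 of 18, 10 of 24 and 11 of 30 (Protocol Table 7, repeated as SAP Table 5). The unacceptable rate is set out as follows: "Mortality of 40% at Day 56 would be considered unexpected and an unacceptable number of excess deaths". The acceptable rate is the historical figure of about 20%.

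Two operating characteristics are claimed in the text. At 20% mortality the trial "will have a 2.6% chance of triggering the stopping rule for mortality". At 40%, "there will be a 71.0% chance of triggering the stopping rule with 30 subjects". Both tables head their probability columns as cumulative.

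Neither document says whether the N subjects must have reached Day 56 before the look, how subjects still in follow-up are counted, or whether enrolment pauses. DMC procedures are left to a charter that is not among the documents.

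**The concern.** A boundary of 4 deaths in 6 has its stated meaning only if all six Day 56 outcomes are known. On the day the sixth subject is accrued, that subject has no follow-up and the few before may be well short of Day 56. The rule would then compare a partial death count with a boundary built for a complete one, and it would cross less often than stated.

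The shortfall is largest at the first look, where the rule could act soonest. A death missed at one look is next counted against a higher boundary. No look is listed after N=30, so on this reading deaths among the first 30 that occur after the last look are never compared with any boundary. This is the only numerical study-level safety stop in the two documents.

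**Working it through.** **Inputs.** Boundaries (N, Xt) = (6, 4), (12, 6), (18, 8), (24, 10), (30, 11), from Protocol Table 7. Day 56 mortality p = 0.20 or 0.40, from Protocol 6.5.4. Outcomes are taken as independent between subjects.

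**Step 1: reproduce the printed figures.** Take each look on its own with all N outcomes known: P(Bin(N, p) ≥ Xt). For N=6, p=0.40: 15(0.4⁴)(0.6²) + 6(0.4⁵)(0.6) + 0.4⁶ = 0.1382 + 0.0369 + 0.0041 = 0.1792.

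- p=0.20: 1.70, 1.94, 1.63, 1.26, 2.56% (printed 1.7, 1.9, 1.6, 1.3, 2.6%).
- p=0.40: 17.92, 33.48, 43.66, 51.09, 70.85% (printed 17.9, 33.5, 43.7, 51.0, 71.0%).

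All agree within 0.2 percentage points. The printed values are therefore complete-data, single-look tails. They are not cumulative: the 20% column falls from 1.9% to 1.6% to 1.3%, which a cumulative probability cannot do.

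**Step 2: upper bound if the look is at accrual.** Subject N contributes no deaths, so at best N−1 subjects have full follow-up: P(Bin(N−1, 0.40) ≥ Xt). For N=6: 5(0.4⁴)(0.6) + 0.4⁵ = 0.0768 + 0.0102 = 0.0870. This bound needs no assumption on accrual speed or timing of deaths.

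**Step 3: size under assumed accrual.** The documents give neither accrual rate nor death timing. Assume exponential death times scaled to 40% by Day 56 and a fixed gap between subjects, and count deaths visible on the day subject N enters (simulation). A gap of 21 days follows from the study dates: November 2014 to December 2017 is 37 months; less 12 months for the last subject leaves 25; 25 × 30.4 / 36 ≈ 21 days. The range shown is 7 to 30 days.

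| N | Printed | Bound, any accrual speed | 21-day gap | 7 to 30 days |
|---|---|---|---|---|
| 6 | 17.9% | 8.7% | 4.4% | 0.3 to 6.2% |
| 12 | 33.5% | 24.7% | 18.6% | – |
| 18 | 43.7% | 36.0% | 30.2% | – |
| 24 | 51.0% | 44.4% | 39.1% | – |
| 30 | 71.0% | 65.7% | 61.4% | about 47 to 64% |

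With deaths spread uniformly over the 56 days instead, the 21-day figure at N=6 is 3.9% and at N=30 about 61%.

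**Step 4: true cumulative probabilities with full follow-up.** Let f_t(k) be the probability of k deaths in the first N subjects with no earlier crossing. Then f_t(k) = Σ_j f_{t−1}(k−j) · P(Bin(6, p) = j), summed over k−j < X_{t−1}. The chance of first stopping at look t is the sum of f_t(k) over k ≥ Xt. Adding over looks:

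- p=0.20: 1.7, 3.0, 3.7, 4.1, 5.3%.
- p=0.40: 17.9, 36.9, 50.3, 59.9, 74.8%.

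**Step 5: cumulative comparison by N=30.** With looks at accrual under constant hazard, the cumulative chance at 40% mortality is about 49% (7-day gap), 64% (21-day) and 67% (30-day), against 74.8%. At 20% mortality and a 21-day gap it is about 2.6%, against 5.3%.

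**The case against.** A reader might infer that the plan prescribes looks before Day 56, so that deaths are certain to be undercounted. The documents do not say this. The word used is after, which sets an order and not a date. The quantity tested is Day 56 mortality, which is not settled until subjects reach Day 56 or die, and the table itself assumes complete data. A look made once those subjects are evaluable is a possible reading, and the unseen DMC charter may fix the timing. That stands: the defect is an unstated look time, and the loss is conditional on looks being made at accrual. A look made between accrual and Day 56 would lose less.

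The literal reading still has support from the drafting. Where completed follow-up is meant, the documents say so: the Day 28 cohort reviews in Protocol 6.1, and the Day 86 safety report and the Day 56 interim analysis in Protocol 13.1. SAP 7.4 adds a timing note for the Day 86 report and none for the mortality rule.

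A reader might also blame timing alone for the printed probabilities not being met. That fails too: even with complete follow-up the rule gives 5.3% and 74.8%. The two problems pull in opposite directions, so the 2.6% reached under a 21-day gap at 20% mortality matches the printed figure only by coincidence.

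Other safeguards exist: DMC monitoring throughout treatment, cohort safety reviews above 10 mg/kg per week, 24-hour SAE reporting, and the sponsor's power to terminate. Deaths would not go unseen, but none of these supplies a numerical boundary.

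**Conclusion.** The concern holds as a missing follow-up condition together with a mislabelled table. It does not show that looks were planned or made before Day 56.

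If looks are taken at accrual, the first look has at most 8.7% single-look chance of crossing at 40% mortality, less than half of the printed 17.9%, and the last at most 65.7% against 71.0%. These bounds rest only on the last-accrued subject having no follow-up and on independent outcomes. The lower figures (0.3% to about 6% at N=6, about 47% to 64% at N=30, about 49% to 67% cumulatively) rest also on the assumed constant hazard and fixed spacing of 7 to 30 days. The loss is severe at the first look and moderate for the rule as a whole unless accrual is fast.

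Separately, and whatever the look timing, the single-look tails should not be labelled cumulative.

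**What to change.** In Protocol 6.5.4 and 13.1 and SAP 7.4, and in the synopsis to match, state that look t is evaluated when all of the first N subjects have reached Day 56 or died. State also that the boundary counts as crossed as soon as deaths by Day 56 among the first N subjects reach Xt. That count cannot fall, so this clause does not change the probabilities and avoids delaying a stop already earned. Say whether enrolment continues while a look is pending.

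In Protocol Table 7, SAP Table 5 and the accompanying text, replace the printed values with the cumulative ones: 1.7, 3.0, 3.7, 4.1, 5.3% at 20% mortality and 17.9, 36.9, 50.3, 59.9, 74.8% at 40%.

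SAP 4.1 records early termination, so the report should also say when each look was made and how many subjects had reached Day 56 or died by then.

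Cost: a few sentences and two tables, with no extra subjects and no change to the boundaries. A scheduled look may fall up to 56 days later, and the stated false-stop rate rises from 2.6% to 5.3%.

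### The mortality rule's table is labelled cumulative but holds single-look binomial tails: at 20% mortality the chance of stopping over the five looks is 5.3%, not 2.6%

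*Protocol*

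**What the plan says.** Protocol 6.5.4 says that "a stopping rule for Day 56 mortality will be applied after every 6 subjects are accrued", and that the study stops at any evaluation where deaths reach the boundary Xt. Table 7 gives the boundaries: 4 of 6, 6 of 12, 8 of 18, 10 of 24 and 11 of 30. The probability columns are headed "Cumulative Probabilities of Stopping at Evaluation (t) with Observed Mortality Rates".

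Two sentences summarise how the rule performs. For the anticipated rate: "A 20% mortality rate, which is anticipated based on historical data, will have a 2.6% chance of triggering the stopping rule for mortality". For 40% mortality: "there will be a 71.0% chance of triggering the stopping rule with 30 subjects". The Synopsis (Statistical Methods) repeats the 71.0% but not the 2.6%. SAP 7.4 repeats both ("will have a 2.6% chance of triggering the stopping rule for mortality" and "there will be a 71.0% chance of triggering the stopping rule with 30 patients"), and SAP Table 5 has the same boundaries and entries as Protocol Table 7.

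**The concern.** The 0.20 column reads 1.7, 1.9, 1.6, 1.3, 2.6%. A probability accumulated over successive looks cannot fall, and this one falls twice. So either the heading or the numbers are wrong. The text then takes the last entry as the chance that the whole rule triggers, without limiting it to the last look.

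These are the only operating characteristics that the two documents give for the study-level mortality rule. The DMC, an ethics committee or an investigator would use them to judge how often a trial running at the expected mortality would be stopped by chance, and how reliably the rule would catch a doubled death rate. If the figures are single-look tails, both chances are understated.

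**Working it through.** **Inputs** (Protocol 6.5.4 and Table 7; identical in SAP 7.4 and Table 5): looks at N = 6, 12, 18, 24, 30; stop if deaths ≥ Xt = 4, 6, 8, 10, 11; assumed Day 56 mortality p = 0.20 or 0.40.

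**Step 1: reproduce the printed figures.** For each look on its own, compute P(X ≥ Xt) with X ~ Binomial(N, p). For example, at N = 6 and p = 0.20:

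15(0.2⁴)(0.8²) + 6(0.2⁵)(0.8) + 0.2⁶ = 0.015360 + 0.001536 + 0.000064 = 0.01696.

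| N | Xt | p = 0.20: single-look | printed | p = 0.40: single-look | printed |
|---|---|---|---|---|---|
| 6 | 4 | 1.696% | 1.7% | 17.920% | 17.9% |
| 12 | 6 | 1.941% | 1.9% | 33.479% | 33.5% |
| 18 | 8 | 1.628% | 1.6% | 43.656% | 43.7% |
| 24 | 10 | 1.262% | 1.3% | 51.092% | 51.0% |
| 30 | 11 | 2.562% | 2.6% | 70.853% | 71.0% |

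Eight of the ten entries agree to the printed decimal. The other two (51.0 and 71.0) are within 0.15 point. Other constructions do not give 2.6%: a strict boundary (more than 11 of 30) gives 0.95%, adding the five tails gives 9.1%, and treating the looks as independent gives 8.8%. The printed values are therefore single-look tails.

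**Step 2: compute the cumulative probability.** Add deaths in blocks of 6. At each look remove the paths that have reached Xt, record their probability as a first stop at that look, and carry the rest forward.

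Look 2 at p = 0.20 shows the method. To stop first at look 2, block 1 must have d = 0 to 3 deaths and block 2 at least 6 − d:

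- d = 0: 0.262144 × 0.000064 = 0.000017
- d = 1: 0.393216 × 0.001600 = 0.000629
- d = 2: 0.245760 × 0.016960 = 0.004168
- d = 3: 0.081920 × 0.098880 = 0.008100

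The sum is 0.01291, so the cumulative chance by 12 subjects is 1.696% + 1.291% = 2.987%. Continuing in the same way:

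| Look (N) | p = 0.20: first stop | cumulative | printed | p = 0.40: first stop | cumulative | printed |
|---|---|---|---|---|---|---|
| 1 (6) | 1.696% | 1.7% | 1.7% | 17.920% | 17.9% | 17.9% |
| 2 (12) | 1.291% | 3.0% | 1.9% | 18.956% | 36.9% | 33.5% |
| 3 (18) | 0.720% | 3.7% | 1.6% | 13.397% | 50.3% | 43.7% |
| 4 (24) | 0.409% | 4.1% | 1.3% | 9.607% | 59.9% | 51.0% |
| 5 (30) | 1.141% | **5.3%** | 2.6% | 14.934% | **74.8%** | 71.0% |

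A simulation of 2,000,000 trials gave 5.24% and 74.8%.

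**Step 3: size of the gap.** At looks 2 to 5 the tables understate the cumulative chance by 1.1, 2.1, 2.8 and 2.7 points at 20% mortality, and by 3.4, 6.6, 8.9 and 3.8 points at 40%. At 20% mortality the five-look total is 5.258/2.562 = 2.05 times the last-look tail. By the second look (3.0%) it already exceeds the 2.6% given for the whole rule, and 4.116/5.258 = 78% of stops come before the only look that the 2.6% describes.

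**The case against.** **The heading may mean something else.** An upper binomial tail on all subjects to date is, loosely, a cumulative probability at that evaluation. On that reading the table is poorly labelled but its contents are nearly right, and relabelling the columns as single-look would repair them. This has some force for the table. It does not rescue the sentence giving 2.6% as the chance of triggering a rule that is applied at five looks.

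**The 71.0% is ambiguous.** It is tied to 30 subjects and could mean the 30-subject look alone, where the exact value is 70.9%. That reading is possible. Under a cumulative heading, however, the figure by 30 subjects is 74.8%.

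**Enrolment may reach 36.** Protocol 6.2 allows up to 36 subjects, and looks come after every 6, but neither table has a boundary at 36. A sixth look could only raise the 5.3%. With assumed boundaries of 12, 13 or 14 at 36, the total would be 7.0%, 5.6% or 5.3% at 20% mortality and 85.9%, 80.3% or 76.7% at 40%. So 5.3% describes the rule as tabulated and should be stated as holding by 30 subjects.

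**The consequence is small.** No boundary or decision changes, the rule stops more readily than stated, no hypothesis test or sample size rests on the figures, a DMC reviews safety independently, and SAP 4.1 records early termination. All of this is true. It limits the urgency but does not make the stated figures correct.

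**Conclusion.** The point holds. On the documents' own boundaries and death rates, the chance that the mortality rule triggers by 30 subjects is 5.3% at 20% mortality, about twice the stated 2.6%. At 40% mortality it is 74.8%, against 71.0%. The 2.6% sentence is wrong as written, and the columns are not cumulative as headed. The 71.0% sentence is wrong if read as cumulative and nearly right if read as the last look only.

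The calculation assumes independent subjects, one common death rate, and Day 56 status known for everyone counted at each look. If death rates differ between dose cohorts, the chance of stopping could lie above or below 2.6%, and nothing is claimed for that case. The boundaries are not shown to be wrong; the stated performance of the rule is. It should be corrected, though no trial decision depends on it.

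**What to change.** - In Protocol Table 7 and SAP Table 5, replace the 0.20 column with 1.7, 3.0, 3.7, 4.1, 5.3% and the 0.40 column with 17.9, 36.9, 50.3, 59.9, 74.8%.
- In Protocol 6.5.4 and SAP 7.4, change 2.6% to 5.3% and 71.0% to 74.8%, both stated as the chance of stopping by 30 subjects. In the Synopsis, change 71.0% to 74.8%.
- Describe the rates as assumed true mortality rates. The header and text call them observed, but the probabilities are computed for a fixed underlying rate.
- Add one line of assumptions: independent subjects, a common death rate, and complete Day 56 status for all counted subjects at each look. Protocol 13.1 ("A stopping rule for excess mortality at Day 56 will be applied after every 6 subjects are accrued") and SAP 7.4 ("A stopping rule for Day 56 mortality will be applied after every 6 patients are accrued") tie the looks to accrual. If a look takes place before those subjects reach Day 56, neither the printed nor the replacement figures describe it, so the sponsor should say which timing the figures assume.

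Relabelling the columns as single-look would be a smaller edit to the table. The 2.6% sentence would still have to change, and the table would no longer show the rule's overall performance by look.

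The cost is a text and table correction, with no change to boundaries, look schedule or data collection. A protocol amendment needs ethics committee re-approval (Protocol 16.1). Because SAP 4.1 records early termination and an abbreviated CSR, correcting the SAP and giving the corrected figures in the CSR is cheaper. The only downside is a less favourable stated chance of stopping at the anticipated mortality.
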